6.1.7.3.3 Survival Follow-up Contacts

Participant survival follow-up status will be assessed approximately every 12 weeks to assess for survival status until death, withdrawal of consent, or the end of the study, whichever occurs first.

The first survival follow-up assessment should be scheduled as described below:

• For participants who discontinue treatment intervention and who will not enter the Efficacy Follow-up Phase, the first survival follow-up contact will be scheduled 12 weeks after the discontinuation visit and/or safety follow-up visit (whichever is last).

For participants who completed assessments in the Efficacy Follow-up Phase, the first survival follow-up contact will be scheduled 12 weeks after the last efficacy assessment follow-up visit has been performed.

6.1.7.3.4 **Post Study**

Participants will be required to return to clinic approximately 14 days after the last dose of study intervention for the poststudy visit. If the poststudy visit occurs less than 14 days after the last dose of study intervention, a subsequent follow-up telephone call should be made at 14 days post the last dose of study intervention to determine of any AEs have occurred since the poststudy clinic visit.

6.2 Adverse Events (AEs), Serious Adverse Events (SAEs), and Other Reportable Safety Events

The definitions of an AE or SAE, as well as the method of recording, evaluating, and assessing causality of AE and SAE and the procedures for completing and transmitting AE, SAE, and other reportable safety event reports can be found in Appendix 5.

Adverse events, SAEs, and other reportable safety events will be reported by the participant (or, when appropriate, by a caregiver, surrogate, or the participant's legally authorized representative).

The investigator and any designees are responsible for detecting, documenting, and reporting events that meet the definition of an AE or SAE as well as other reportable safety events. Investigators remain responsible for following up AEs, SAEs, and other reportable safety events for outcome.

The investigator, who is a qualified physician, will assess events that meet the definition of an AE or SAE as well as other reportable safety events with respect to seriousness, intensity/toxicity and causality.

6.2.1 Time Period and Frequency for Collecting AE, SAE, and Other Reportable Safety Event Information

All AEs, SAEs and other reportable safety events must be reported starting after the first dose of study intervention on C1D1. AEs, SAEs, and other reportable safety events that occur after the consent form is signed but before first dose of study intervention must be reported by the investigator only if the participant is receiving other run-in treatment, if the event causes the participant to be excluded from the study, or is the result of a protocol- specified intervention, including but not limited to washout or discontinuation of usual therapy, diet, or a procedure.

• All AEs from the first dose of study intervention through 30 days following cessation of study intervention or until initiation of new anticancer therapy, whichever is earlier, must be reported by the investigator.

54

Confidential

- All AEs meeting serious criteria, from the first dose of study intervention through 90 days following cessation of study intervention or 30 days following cessation of study intervention if the participant initiates new anticancer therapy, whichever is earlier, must be reported by the investigator.
 - Of note, progression of disease under study does not meet the definition of an Adverse Event, therefore death due to progression of disease under study is not reportable as an SAE.
- All pregnancies and exposure during breastfeeding, from the first dose of study intervention through 120 days following cessation of study intervention, or 30 days following cessation of study intervention if the participant initiates new anticancer therapy must be reported by the investigator.
- Additionally, any SAE brought to the attention of an investigator at any time outside of the time period specified above must be reported immediately to Merck if the event is considered drug-related.

Investigators are not obligated to actively seek AEs or SAEs or other reportable safety events in former study participants. However, if the investigator learns of any SAE, including a death, at any time after a participant has been discharged from the study, and he/she considers the event to be reasonably related to the study intervention or study participation, the investigator must promptly notify Merck.

All initial and follow-up AEs, SAEs, and other reportable safety events will be recorded and reported to Merck within the time frames as indicated in Table 7 via fax (Attn: Worldwide Product Safety; [contact]).

Type of Event	Reporting Time Period: Consent to First Dose of Study Intervention	Reporting TimePeriod:First Dose ofStudyInterventionthrough Protocol-specified Follow-up Period	Reporting Time Period: After the Protocol- specified Follow-up Period	Time Frame to Report Event and Follow-up Information to Merck:
Serious Adverse Event (SAE) including New Cancer Diagnosis and Overdose	Report if: - due to protocol- specified procedure/interve ntion - causes exclusion - participant is receiving other run-in treatment	Report all	Report if: - drug/vaccine related. (Follow ongoing to outcome)	Within 2 business days but no longer than 3 calendar days of learning of event
Pregnancy/Lactation Exposure	Report if: - due to intervention - causes exclusion	Report all	Previously reported – Follow to completion/termination; report outcome	Within 2 business days but no longer than 3 calendar days of learning of event

Table	7 Reporting	Time	Periods	and	Time	Frames	for	Adverse	Events	and	Other	Reportabl	e
Safety	Events												

Event of Clinical Interest (require regulatory reporting)	Report if: - due to intervention causes exclusion	Report - potential drug- induced liver injury (DILI) require regulatory reporting	Not required	Within 2 business days but no longer than 3 calendar days of learning of event
---	--	--	--------------	--

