Tumor Imaging (chest, abdomen, & pelvis) and iRECIST Assessment Note: Imaging of the brain required only at screening.		Х							X		Х	X	X		X		Imaging is performed at Screening, Week 9 and every 9 weeks (± 7 days) during Year 1. After Year 1, imaging is performed every 12 weeks (±7 days). This schedule will be maintained regardless of treatment delays.

Confidential

Study Period:	Scre	ening			Ι	nterve	ention	(21-D	ay Cy	cles)				Post	treatment Vis	sits	Notes
Visit Number/Title:	1/Scro	eening	1	C1	15	(22	C3	C4	C5	C6 to C35	\geq C36	End of Treatment	Safety Follow-	Efficacy Follow-	Survival	
Scheduling Window (days)	-42 to - 1	-28 to - 1	±3	8 ±3	±3	±3	±3	±3	±3	±3	±3	±3	At time of treatment discontin uation	Approx. 30d after last dose (± 7d)	up Q6W (Y1) or Q9W (Y2+) (± 7d)	Q12W ^a (± 14d)	
Safety Procedures	1	1	r –	1	r	r –	r	r –	r –	1		r	1	1	1	Γ	
AE/SAE Review	x	x	x	x	x	x	x	x	x	x	x	x	x	х	х		Report AEs occurring within 30 days after the last dose of study intervention. Report SAEs occurring within 90 days after the last dose of study intervention, or 30 days after the last dose of study intervention if a new anticancer therapy is initiated, whichever is first.
Full Physical Examination		Х											X				
Height		Х															
Directed Physical Examination			X		Х	X	Х	X	X	Х	Х	Х		Х			
Contact				x													The investigator or medically qualified designee (consistent with local requirements) will assess participants for development of early toxicity. An unscheduled visit can occur before C1D15 if necessary for safety.

Study Period	Scre	ening			I	nterve	ntion	(21-D	av Cv	cles)				Post tr	eatment Visi	its	Notes
Study Ferrou.	Sere	creening In					ntion				C6		_End of	1 050 0			10005
Vigit Number/Title:	1/50%	onina		C1		0	r'n	C2	C4	C5	to	\geq	Treatment	Safety	Efficacy	Second and	
Cvcle Dav	1/501	Jenning	1	8	15	1	15	1	1	1	1	1		Follow-	Follow-	FU	
Scheduling Window (days)	-42 to - 1	-28 to - 1	±3	±3	±3	±3	±3	±3	±3	±3	±3	±3	At time of treatment discontin uation	Approx. 30d after last dose (± 7d)	Q6W (Y1) or Q9W (Y2+) (± 7d)	Q12W ^a (± 14d)	
Vital Signs (resting BP, heart rate, RR, and temp) and weight		х	x		x	x	х	х	x	х	Х	Х	X	х			The Day 15 visit is mandatory for C1 and C2. During C3 and subsequent cycles, participants may return for the D15 visit if BP monitoring is required.

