5.2.1 Timing of Dose Administration

Trial interventions should be administered on Day 1 of each cycle after all procedures/assessments have been completed as detailed on the Schedule of Activities, Section 2.3. Trial interventions may be administered up to 3 days before or after the scheduled Day 1 of each cycle due to administrative reasons.

All trial interventions will be administered on an outpatient basis.

Pembrolizumab 200 mg will be administered as a 30 minute IV infusion every 3 weeks. Sites should make every effort to target infusion timing to be as close to 30 minutes as possible. However, given the variability of infusion pumps from site to site, a window of -5 minutes and +10 minutes is permitted (i.e., infusion time is 30 minutes: $-5 \min/+10 \min$).

The Pharmacy Manual contains specific instructions for the preparation of the pembrolizumab infusion fluid and administration of infusion solution.

Lenvatinib 20 mg will be administered in an oral dose to be taken once daily. Capsules are packaged in cold form blisters or high-density polyethylene bottles with a polypropylene cap and desiccant. The blisters and bottles should be stored under room temperature.

AEs associated with pembrolizumab exposure, including coadministration with additional compounds, may represent an immunologic etiology. These immune-related AEs (irAEs) may occur shortly after the first dose or several months after the last dose of pembrolizumab/combination treatment and may affect more than one body system simultaneously. Therefore, early recognition and initiation of treatment is critical to reduce complications. Based on existing clinical study data, most irAEs were reversible and could be managed with interruptions of pembrolizumab/combination treatment, administration of corticosteroids and/or other supportive care. For suspected irAEs, ensure adequate evaluation to confirm etiology or exclude other causes. Additional procedures or tests such as bronchoscopy, endoscopy, skin biopsy may be included as part of the evaluation. Dose modification and toxicity management guidelines for irAEs associated with pembrolizumab/combination treatment are provided in Table 4.

Attribution of Toxicity:

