6.1.7.3.1 Safety Follow-Up Visit

The mandatory Safety Follow-Up Visit should be conducted approximately 30 days after the last dose of study intervention or before the initiation of a new anti-cancer treatment, whichever comes first.

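### Patients who stop for progression and start no new therapy have no scheduled SAE inquiry between about day 30 and the day-90 end of the SAE reporting window

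*Combined protocol and SAP*

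**What the plan says.** **Reporting windows.** Section 6.2.1 requires SAEs to be reported "through 90 days following cessation of study intervention". The same sentence shortens the window for patients who go on to another treatment: "30 days following cessation of study intervention if the participant initiates new anticancer therapy, whichever is earlier". The note on the AE/SAE row of the Schedule of Activities (Section 2.3, Table 1) agrees: "Report SAEs occurring within 90 days after the last dose of study intervention". Non-serious AEs are collected only "through 30 days following cessation of study intervention or until initiation of new anticancer therapy, whichever is earlier".

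**Scheduled reviews.** The AE/SAE row is marked from Screening through Efficacy Follow-up. The Survival FU cell is blank. Section 6.1.7.3.1 states: "The mandatory Safety Follow-Up Visit should be conducted approximately 30 days after the last dose of study intervention". The Schedule gives that visit a window of ±7 days.

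**Who is seen afterwards.** Under Section 6.1.7.3.2, Efficacy Follow-up is for patients who complete treatment or stop for a reason other than progression. For patients who do not enter it, Section 6.1.7.3.3 says that "the first survival follow-up contact will be scheduled 12 weeks after the discontinuation visit and/or safety follow-up visit (whichever is last"). The stated purpose of these contacts is survival status, and the Schedule gives them ±14 days.

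**Late events.** Section 5.2.1 warns that immune-related events may appear as late as "several months after the last dose of pembrolizumab/combination treatment".

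**The concern.** The plan sets a mandatory 90-day SAE window but gives one group of patients no scheduled occasion on which anyone asks about its last two-thirds. Section 5.2.1 expects immune-related events in that span. Section 6.2.2 prefers direct, open-ended questioning as the way to detect events. After day 30 that questioning is scheduled for patients in Efficacy Follow-up but not for those who stopped for progression.

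Safety and tolerability is a secondary objective with adverse events as an endpoint (Section 3.2). Two things are at stake: completeness of SAE capture between day 30 and day 90, and evenness of capture, because ascertainment would depend on why the patient stopped. PFS, response rate, overall survival, and the endpoint on treatment interruption, reduction and discontinuation are not affected.

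**Working it through.** The documents state no figure on this point to reproduce. The check is calendar arithmetic on the protocol's own visit times, in days after the last dose.

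**Inputs**
- SAE window: 90 days; 30 days if new anticancer therapy starts (Sections 6.2.1 and 2.3).
- Safety visit: day 30 ± 7, so day 23 to 37 (Sections 6.1.7.3.1 and 2.3).
- First survival contact: 12 weeks = 84 days after the later of the discontinuation and safety visits (Section 6.1.7.3.3), ± 14 days (Section 2.3). The safety visit is taken as the later one. If the discontinuation visit were later, the contact would be later still.
- AE/SAE row: 15 marks across 16 visit columns (2 screening, 10 treatment, end of treatment, safety, efficacy, survival). The unmarked column is Survival FU.

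**First scheduled contact after the safety visit** = safety visit day + 84 (± 14)
- Nominal: 30 + 84 = day 114
- Earliest: 23 + 84 − 14 = day 93
- Latest: 37 + 84 + 14 = day 135

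Even with every window used in the favourable direction, the contact falls after day 90.

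**SAE days after the last scheduled review** = 90 − safety visit day

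| Safety visit | Uncovered days | Share of 90 days |
|---|---|---|
| Day 23 | 67 | 74% |
| Day 30 | 60 | 67% |
| Day 37 | 53 | 59% |

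**Comparison group.** Counting from the last dose (an assumption, since the anchor is not stated), Efficacy Follow-up reviews fall at about days 42 and 84 on the 6-week schedule of Section 6.1.7.3.2, or about day 63 on the 9-week imaging schedule of Section 6.1.4.3. Either way at least one review falls inside the window. A patient who progresses in Efficacy Follow-up at, say, day 42 would next be contacted at 42 + 84 = day 126, leaving 90 − 42 = 48 days uncovered.

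**Provisions that might close the gap**
- The poststudy visit or call (Section 6.1.7.3.4) is at about day 14.
- The Schedule allows survival-status contact at any time, but this is optional.
- Sections 5.4 and 6.1.6.1 keep discontinued patients in follow-up, but according to the same Schedule.
- Section 6.2.3 requires follow-up at later visits or contacts after an initial report. It creates no new contact.
- Repeat imaging at 4 to 8 weeks in clinically unstable patients (Table 6) is at the investigator's discretion.

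None of these schedules an SAE inquiry between day 30 and day 90.

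**Illustrative size.** The documents give neither the affected share nor the SAE rate. Assume that a fraction f of the 30 patients stops for progression without new therapy, and that each has SAE risk q in days 30 to 90. Expected SAEs in the gap = 30 × f × q:
- f = 20%, q = 2%: 0.12
- f = 40%, q = 5%: 0.6
- f = 60%, q = 10%: 1.8

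These are events occurring in the gap, not events missed; some would come to attention anyway. One missed patient with an SAE would be 1/30 = 3.3% of the planned sample.

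**The case against.** The strongest reply is that the reporting duty is intact. Section 6.2 makes investigators responsible for detecting and reporting these events, and Section 5.4 says that stopping treatment is not withdrawal. Patients with an ongoing event are followed to outcome, ad hoc contact is allowed, and SAEs that come to notice must be reported. The affected group is limited and the likely count small. All of this stands. It limits the point to a risk of under-counting, but it does not supply a scheduled inquiry.

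Several stronger readings are tempting and not supported:
- **That most patients are affected.** Once new anticancer therapy starts, the SAE window ends at day 30, about when the safety visit falls. Only progressors without new therapy are concerned, and their share is not given.
- **That the PFS figures supply that share.** In Section 7.2, 3.5 months is a historical anti-PD-1 figure and 6 months an interim stopping threshold. Neither is an assumption for this regimen, and PFS events include deaths.
- **That these patients have no contact, or that SAEs will certainly be missed.** The documents show only that no contact is scheduled.
- **That investigators are released from asking.** Section 6.2.1 does say "Investigators are not obligated to actively seek AEs or SAEs or other reportable safety events in former study participants", but the sentence after it speaks of patients discharged from the study. Patients in survival follow-up are still on study.
- **That a contact after day 90 is itself the fault.** A later contact could ask retrospectively about days 30 to 90. The fault is that no scheduled contact asks.

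**Conclusion.** The concern holds in a limited form. For patients who stop for progression and start no new anticancer therapy, about 60 of the 90 SAE days (53 to 67) follow the last scheduled AE/SAE review. The next scheduled contact, at about day 114 (93 to 135), does not ask about SAEs. Capture is passive for them and active for patients in Efficacy Follow-up, so late immune-related SAEs are at risk of being under-counted, and unevenly by reason for stopping.

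The timing follows from the protocol's own visit rules and the blank Survival FU cell. The size does not: 0.1 to 1.8 SAEs in the gap rests wholly on the assumed ranges above. The effect on the safety results is probably small, but the mismatch is real and cheap to remove.

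The group may be wider. The Trial Summary (Section 1.0) gives post-treatment follow-up to patients who stop for reasons other than progression or treatment-related toxicity, whereas Section 6.1.7.3.2 leaves out only progressors. If the Trial Summary governs, patients who stopped for toxicity have the same gap.

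**What to change.** In the Schedule of Activities, and to match in Section 6.1.7.3.3, schedule an SAE inquiry covering days 30 to 90 for patients who are not in Efficacy Follow-up and have not started new anticancer therapy. There are two options:
- **Preferred:** a telephone contact at day 90 (+7 days) after the last dose, with AE/SAE review marked. The span not covered by any scheduled inquiry falls from about 60 days to 0. The cost is one short call per affected patient and one mark in the Schedule.
- **Minimum:** mark AE/SAE review at the first survival contact, with explicit retrospective questions about SAEs up to day 90. This adds no contact, but recall is longer (contact at about day 114, up to day 135), and a patient who has died by then cannot be asked.

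Also reconcile the Trial Summary with Section 6.1.7.3.2 on whether patients who stop for treatment-related toxicity enter post-treatment follow-up, and apply the same inquiry to any who do not. Neither change alters a dose, a treatment rule or an efficacy analysis.

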6.2.2 Method of Detecting AEs, SAEs, and Other Reportable Safety Events

Care will be taken not to introduce bias when detecting AEs and/or SAEs and other reportable safety events. Open-ended and nonleading verbal questioning of the participant is the preferred method to inquire about AE occurrence.

6.2.3 Follow-up of AE, SAE, and Other Reportable Safety Event Information

After the initial AE/SAE report, the investigator is required to proactively follow each participant at subsequent visits/contacts. All AEs, SAEs, and other reportable safety events including pregnancy and exposure during breastfeeding, events of clinical interest (ECIs), cancer, and overdose will be followed until resolution, stabilization, until the event is otherwise explained, or the participant is lost to follow-up. In addition, the investigator will make every attempt to follow all nonserious AEs that occur in allocated or randomized participants for outcome. Further information on follow-up procedures is given in Appendix 5.

6.2.4 Sponsor Responsibility for Reporting Adverse Events

All Adverse Events will be reported to regulatory authorities, IRB/IECs and investigators in accordance with all applicable country specific regulatory requirements, global laws and regulations.

6.2.5 Pregnancy and Exposure During Breastfeeding

Although pregnancy and infant exposure during breastfeeding are not considered AEs, any pregnancy or infant exposure during breastfeeding in a participant (spontaneously reported to the investigator or their designee) that occurs during the study are reportable to Merck.

All reported pregnancies must be followed to the completion/termination of the pregnancy. Pregnancy outcomes of spontaneous abortion, missed abortion, benign hydatidiform mole, blighted ovum, fetal death, intrauterine death, miscarriage, and stillbirth must be reported as serious events (Important Medical Events). If the pregnancy continues to term, the outcome (health of infant) must also be reported.

6.2.6 Events of Clinical Interest (ECIs)

Selected nonserious and SAEs are also known as ECIs and must be reported to Merck.

Events of clinical interest for this study include:

- 1. An overdose of pembrolizumab that is not associated with clinical symptoms or abnormal laboratory results. For purposes of this study, an overdose of pembrolizumab will be defined as any dose of 1,000 mg or greater (\geq 5 times the indicated dose). No specific information is available on the treatment of overdose of pembrolizumab. In the event of overdose, the participant should be observed closely for signs of toxicity. Appropriate supportive treatment should be provided if clinically indicated. If an adverse event(s) is associated with ("results from") the overdose of a Merck product, the adverse event(s) is reported as a serious adverse event, even if no other seriousness criteria are met.
- 2. For the purpose of this study, an overdose will be defined as any dose exceeding the prescribed dose for:
 - Lenvatinib: any dose above the protocol-prescribed dose if associated with an adverse event

There is no specific antidote for an overdose of lenvatinib. Due to its high degree of plasma protein binding, lenvatinib is not expected to be dialyzable. Adverse reactions in patients receiving single doses of lenvatinib as high as 40 mg were similar to those in clinical studies at the recommended dose for differentiated thyroid cancer, RCC, and HCC.

3. An elevated AST or ALT lab value that is greater than or equal to 3X the upper limit of normal and an elevated total bilirubin lab value that is greater than or equal to 2X the upper limit of normal and, at the same time, an alkaline phosphatase lab value that is less than 2X the upper limit of normal, as determined by way of protocol-specified laboratory testing or unscheduled laboratory testing.*

*Note: These criteria are based upon available regulatory guidance documents. The purpose of the criteria is to specify a threshold of abnormal hepatic tests that may require an additional evaluation for an underlying etiology.

